4.4 Applicable Endpoint Definitions

Access Abandonment (permanent abandonment) is defined as the point at which the access can no longer be used for one or two needle prescribed HD as it may be unable to provide adequate flows and / or is deemed unsafe for the participant, and the associated problem cannot be corrected by any further intervention, including medical, surgical, or endovascular interventions or rest.^{8,19} Participants with an abandoned index AVF will continue with follow-up through 24-months and data will be collected on safety and interventions.

A HD AV access is not considered abandoned:

- If the participant discontinues use of the AV access due to kidney transplant, initiation of PD, or participant preference.
- During the maturation period or while waiting for a second stage procedure unless the principal investigator (PI) determines the participant requires and they then receive an alternative HD vascular access.

- During planned interventions, including transposition.
- If all reasonable efforts have not been attempted (and documented) to improve the condition of the access for it to be used.

A discontinuation of use of the clinical investigation AVF for any reason that does not meet this definition of access abandonment will be considered a temporary interruption.

Access Circuit Censoring Events include participant transfer to PD, kidney transplantation or the event of a participants premature discontinuation in the investigation due to withdrawn consent, withdrawal by PI, Lost to Follow-Up (LTF), or participant death (refer to Section 6.5 for definitions).

Adjunctive Procedure(s): Procedure(s) completed during the index procedure (prior to leaving the procedure room) as part of Standard-of-Care (SOC) procedures. These may include procedures to facilitate maturation and / or cannulation of the AVF, procedures to maintain use of the AVF, procedures to ensure HD continuity, as well as procedures to address AFs.

Second Stage Procedure(s): Facilitation Interventions (as defined below) intended to support the cannulation of arterialized vein segments that are determined to be needed a priori to or at the time of the index procedure (i.e. pre-planned facilitation interventions intended to support cannulation). Second stage procedures will not count against the intervention or patency endpoints and will require completion of the Second Stage Procedures eCRF.

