## 2.7 Endpoints

Note: The term access abandonment is synonymous with permanent abandonment for the purposes of these investigation documents. Access abandonment (permanent abandonment) is an abandonment that meets the definition in Section 4.4 of the CIP. The term access discontinuation is used to refer to any discontinuation of use of the access that does not meet these criteria of the definition and may also be referred to as a "temporary interruption" as per the CIP.

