#### 5.2.3 Cannulation Success

Cannulation success is defined as with successful first use for HD using 2-needle cannulation. This endpoint will be evaluated through 6 months. Additionally, for exploratory purposes, the endpoint will be evaluated through 30 days, 6 weeks, 3 months, 12 months, 18 months, and 24 months.

The event of cannulation success will be identified if:

On the EndoAVF Dialysis page, "Date endoAVF First Used with 2 Needles for Hemodialysis" is not NULL and within a specific visit (e.g., within 210 days for 6 months post creation).

Kaplan-Meier (KM) analysis will be used to estimate the time from HD AV access creation (the date of index procedure) to first successful use for HD using 2-needle cannulation through certain post creation visit.

- If cannulation success occurs, the participant is considered as having the event at the corresponding date.
- If the participant was transferred to PDs, or had a kidney transplant, or had access discontinuation, or discontinued before the end of a specific visit window (e.g.180+30 = Day 210 for 6-month visit) without cannulation success, the participant is considered as censored at the earliest date among these events (i.e. PD start date, kidney transplant date, date of access discontinuation, or last date of available study data including the unscheduled visit date).
- Otherwise, if the participant did not achieve cannulation success and has passed the specific visit window by the cutoff date of database lock, the participant will be censored at the end of the reporting time window (e.g., 180+30 = Day 210 for the 6-month reporting, 730+30 = 760 for the 24-month reporting) for this analysis. If the participant had access permanent abandonment prior to achieving cannulation success and has passed the specific visit window by the cutoff date of database lock, the participant will be censored at the date of permanent abandonment.

This endpoint will be evaluated on the AT population. The number of participants with events, number of participants censored, time to event (days), and proportion of participants with events along with the 95% CI will be presented at 6-months post creation using the KM method. For the 6-month reporting, the cannulation success rate up to 6-months (up to Day 210) will be presented. For the final reporting, the cannulation success rate up to 24-months (up to Day 760) will be presented.

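### Cannulation success (SAP 5.2.3) censors participants at permanent abandonment before first use, so the Kaplan-Meier success rate is too high whenever a cannulation follows such an abandonment

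*SAP*

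**What the plan says.** Protocol 4.2.2 defines cannulation success both as a time from access creation to first successful two-needle use and as the proportion of participants who reach it, assessed through 6 months. Protocol 7.5 makes the secondary endpoints descriptive and calls for KM for time-to-event endpoints.

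SAP 5.2.3 applies KM in the As-Treated population with Day 210 as the 6-month limit. Non-successes fall into three groups:

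- Transfer to peritoneal dialysis (PD), transplant, access discontinuation or early exit: censored at the earliest of "PD start date, kidney transplant date, date of access discontinuation, or last date of available study data including the unscheduled visit date". Permanent abandonment is not among these dates.
- Never cannulated but past the window: censored at the end of the reporting window, so at risk throughout.
- Abandoned before success: the condition of the rule reads "If the participant had access permanent abandonment prior to achieving cannulation success and has passed the specific visit window". Its consequence for anyone who meets that condition is stated as "by the cutoff date of database lock, the participant will be censored at the date of permanent abandonment".

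Protocol 4.4 describes permanent abandonment as a state in which "the associated problem cannot be corrected by any further intervention, including medical, surgical, or endovascular interventions or rest". Follow-up does not stop there: "Participants with an abandoned index AVF will continue with follow-up through 24-months and data will be collected on safety and interventions".

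SAP 5.3.4 (functional maturation) and 5.3.5 (functional HD usability) repeat the rule. SAP 5.2.2 (physiological maturation, a binary analysis) counts abandonment before maturation, in participants who have passed the window, as not having the event.

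**The concern.** KM treats a censored participant as someone whose later course is unknown but exchangeable with those still at risk. An abandoned fistula is neither. Under the protocol's definition it cannot later be cannulated, and the participant's status is known because follow-up continues. Censoring at abandonment takes a certain non-success out of the denominator of every later event.

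Within SAP 5.2.3, a fistula that is never used but not formally abandoned stays at risk to Day 210, while one that has definitely failed leaves the risk set. The definite failure is handled more favourably than the uncertain one.

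At stake is the 6-month cannulation success rate and its confidence interval, a named secondary effectiveness result. The proportion that protocol 4.2.2 asks for is not what this rule estimates.

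**Working it through.** The documents give no planned cannulation rate for this trial, so there is no plan figure to reproduce.

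**Direction.** KM success is 1 − ∏(1 − dᵢ/nᵢ), where dᵢ is the number cannulated and nᵢ the number at risk at each cannulation time. Removing participants who cannot succeed lowers nᵢ at every later time and leaves dᵢ unchanged. Each factor falls or stays the same, so the estimate rises or stays the same. It rises exactly when at least one cannulation follows.

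**Hand example** (N = 150, no exits: 60 cannulated, then 15 abandoned, then 48 cannulated, 27 never).

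- Observed proportion: (60 + 48)/150 = 72.0%.
- SAP rule: 75 at risk at the second step, so 1 − (90/150)(27/75) = 1 − 0.60 × 0.36 = 78.4%.
- Abandoned kept at risk: 1 − (90/150)(42/90) = 72.0%.
- If 3 of the 15 leave after the last cannulation but before Day 210, the literal rule keeps those 3 at risk: 1 − (90/150)(30/78) = 76.9%.
- If all 15 abandonments came after the last cannulation, both rules would give 72.0%.

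**Size under stated assumptions.** From the documents:

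- Pre-market time to cannulation, mean 2.0 and SD 1.6 months (protocol 2.1.2).
- Attrition of 20% by 6 months (protocol 7.3, SAP 2.4).
- Day 210 limit (SAP 5.2.3).

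Assumed:

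- Lognormal shape for time to cannulation.
- Abandonment before use spread evenly over months 0 to 6.
- 20% of the rest never cannulated.
- Exits independent of outcome.

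For the lognormal, σ² = ln(1 + (1.6/2.0)²) = 0.495 and μ = ln 2.0 − σ²/2 = 0.446. Day 210 is 6.90 months, so F = Φ((ln 6.90 − 0.446)/0.703) = 0.983. The true proportion is (1 − a) × 0.80 × 0.983, where a is the share abandoned. The SAP value comes from simulating 1,000,000 participants under the literal rule.

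| Abandoned before use | True | SAP rule | Overstatement |
|---|---|---|---|
| 5% | 74.7% | 76.4% | 1.7 points |
| 10% | 70.8% | 74.1% | 3.3 points |
| 22.7% | 60.8% | 67.6% | about 6.7 points |

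Keeping the abandoned at risk returned the true value within 0.1 point in each row.

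The 22.7% is 100 − 77.3, from the pre-market 6-month cumulative patency in protocol 2.1.2. The same section gives 100% functional patency among those who used the fistula, which suggests that losses came mainly before use.

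For scale, the 95% half-width at N = 150 and 72% is 1.96 × √(0.72 × 0.28/150) = 7.2 points.

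**Limit of the simple repair.** If abandoned participants move to PD and are censored there, the risk-set rule is also too high. In the 10% case with half of them moving within 1 month (assumption): true 70.8%, SAP rule 74.0%, risk-set rule 72.3%, cumulative incidence 70.8%. If all of them move: 70.8%, 73.9%, 73.9% and 70.8%.

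**The case against.** Several points on the other side stand, and they limit the finding.

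- **KM is what the protocol asks for.** Protocol 7.5 names it for time-to-event endpoints. The fault is in who is censored, not in using KM, and the main repair should stay within KM.
- **Formal abandonment is narrow.** Protocol 4.4 does not count an access as abandoned "During the maturation period or while waiting for a second stage procedure unless the principal investigator (PI) determines the participant requires" and then receives another access. It also requires that reasonable efforts have been made and documented. Fistulas that fail without meeting this definition already stay at risk to Day 210 and are handled correctly.
- **The endpoint is descriptive.** Event and censored counts accompany the rate, and SAP 6.16 summarises abandonment separately. The counts do not repair the rate, however: events divided by N is 66.1% in the 10% case, too low because of attrition.
- **The contrast with SAP 5.2.2 is weak evidence**, since one analysis is binary and the other time-to-event.
- **Appendix 2 may settle details.** The derived-data specification is listed but is not in the text available. It could resolve how participants who abandon and then leave are treated.

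A reader might infer that the SAP breaches the protocol's censoring list. It does not: the wording is "Access Circuit Censoring Events include participant transfer to PD, kidney transplantation or the event of a participants premature discontinuation in the investigation", an open list, which the endpoint definitions invoke for the patency endpoints. Nor does the point extend to censoring at access discontinuation, which SAP 2.7 keeps apart: "The term access discontinuation is used to refer to any discontinuation of use of the access that does not meet these criteria".

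**Conclusion.** The rule is wrong as written for the proportion that protocol 4.2.2 asks for. The direction is certain: never too low for this reason, and too high whenever a success follows a permanent abandonment before success. The size is not certain. It is about 1.7 to 3.3 points for 5% to 10% abandoned before use, and about 6.7 points at 22.7%, under the assumptions given in the check.

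The 22.7% case should be read as an upper indication and not as an expected abandonment rate. The pre-market definitions are not shown, and protocol 2.1.1 reports one abandonment after a cannulation-induced injury, so not every loss need precede use. Later abandonment gives a smaller bias, and none if it all follows the last cannulation.

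A reader might also infer that the trial's conclusions are at risk. The documents do not support that: both hypothesis tests concern other endpoints, and no test, alpha or power depends on this rate. The change should be made because a systematic error in a reported secondary rate can be avoided with data already collected.

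**What to change.** In SAP 5.2.3, and likewise in 5.3.4 and 5.3.5:

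1. **Main analysis, within KM.** Keep every participant with permanent abandonment before success in the risk set as a non-success to the end of the reporting window (Day 210 or Day 760), or to their own later protocol 4.4 censoring event if that is earlier. Apply this whether or not they passed the visit window.
2. **Identification.** Use the abandonment criteria in SAP 5.3.7. Those in 5.2.4 require prior two-needle use and cannot detect abandonment before use.
3. **Supportive analyses.** Add a cumulative incidence with abandonment as the competing event, to cover transfer to PD after abandonment. Making it the main estimate would need an amendment of protocol 7.5 or a justified departure from it. Keep the current KM for comparison with the pre-market 84.9%, noting that this figure is for the HD subset and SAP 5.2.3 uses the As-Treated population.
4. **Clarification.** State in the derived-data specification how participants who abandon and then leave before the window ends are handled.

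Censoring for participants without abandonment stays as it is. The cost is one sentence in each of three sections, a status-flag change, and matching updates to the table shells and derived-data specification. With the KM-based main analysis no protocol change is needed. The reported rate becomes somewhat less favourable.

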#### **5.2.4** Cumulative Functional Patency

The time interval of cumulative functional patency is defined as the time from first successful HD AV access use for HD using 2-needle cannulation to access abandonment. This endpoint will be evaluated through 12-months. Additionally, for exploratory purposes, the endpoint will be evaluated through 6 months, 18 months, and 24 months.

Only the participants who have started 2-needle HD using the endoAVF will be considered as evaluable for this endpoint.

Access Abandonment (Permanent Abandonment) will be identified if:

On the EndoAVF Dialysis page, Date endoAVF Successfully Used with 2 Needles for Hemodialysis is not NULL and within a specific visit (e.g., within 395 days for 12 months).

and

On the EndoAVF Abandonment page, Date of Abandonment is not NULL and within a specific visit (e.g. within 395 days for 12 months), the question of "All Possible Attempts Have Been Made to Improve the Condition of the Access" is checked as Yes, and the question of "Could Further Endovascular Interventions

Salvage the Access" is checked as No, and the question of "Could Further Surgical Revisions Salvage the Access?" is checked as No, and Reason for Abandonment is selected as "The Access is No Longer Viable" or "The Access is Viable but there are Complications that Require the Abandonment of the Access".

The binary definition for cumulative functional patency is shown as below:

- If permanent abandonment, as detailed above, occurs on, or before, a specific visit (e.g., 365+30 = Day 395 for 12 months post creation), the participant is considered as having an event (loss of cumulative functional patency).
- If the participant was transferred to PD, or had a kidney transplant, or had access discontinuation, or discontinued before the beginning of a specific visit (e.g., 365-30 = Day 335 for 12 months post creation) without permanent abandonment, the participant is considered not evaluable and will not be included in the analysis.
- Otherwise, if the participant did not have permanent abandonment and has passed the specific visit window by the cutoff date of database lock, the participant is considered as not having an event.

This endpoint will be evaluated on the AT population and on the AT population with attainment of first successful HD AV access use for HD using 2-needle cannulation (on the EndoAVF Dialysis page, Date endoAVF Successfully Used with 2 Needles for Hemodialysis is not NULL). The proportion of cumulative functional patency (100% - event rate) and the 95% two-sided CI will be provided using the Clopper-Pearson method. For the 6-month reporting, the cumulative functional patency rate will be presented for 6-months (up to Day 210). For the final reporting, the physiological maturation rate up to 24-month (up to Day 760) will be presented.

## 5.3 Exploratory Endpoints

#### 5.3.1 Procedure Success

Procedure success is defined as successful endoAVF creation. The event of procedure success will be identified if:

On the Procedure Overview page, the question of "Was WavelinQ endoAVF Successfully Created?" is checked as Yes, and the question of "Was Final Result Confirmed via Angiography or Duplex Ultrasound?" is also checked as Yes.

This endpoint will be evaluated on the ITT population. The proportion of participants with procedure success will be reported with the 95% two-sided CI using the Clopper-Pearson method.

#### 5.3.2 Adjunctive Procedure

A participant is considered of having adjunctive procedure if:

On the Adjunctive Procedures page, Treatment is not null.

This endpoint will be evaluated on the AT population. The number and proportion of participants with adjunctive procedures, total number of procedural adjunctive procedures, and the number and proportion of each treatment type of adjunctive procedure will be reported.

#### 5.3.3 Vascular Access at HD Initiation

The vascular access HD modality used at the initiation of HD following the index procedure is captured on the Dialysis History/Onset page. To get the data needed for this calculation, the question of "If the subject is not currently on Hemodialysis, did the subject start hemodialysis during the study?" is YES and Start Date of Dialysis is not NULL, and Vascular Access Used for First Dialysis Session is not NULL. When endoAVF is selected for

Vascular Access Used for First Dialysis Session, the 1- or 2-needle cannulation information will be obtained from the EndoAVF Dialysis page. When the question of "Was endoAVF First Used with 1-Needle for Hemodialysis" is checked as Yes and the corresponding date is not NULL, it is considered as 1-Needle cannulation. When the question is checked as No and Date endoAVF Successfully Used with 2 Needles for Hemodialysis is not NULL, it is considered as 2-Needle cannulation.

This endpoint will be evaluated on the AT Incident population. The total number of all types of vascular accesses and proportion of each type will be reported. For Study endoAVF, the proportions of 1-Needle and 2-Needle cannulation will also be provided.

#### 5.3.4 Functional Maturation

Functional maturation is defined as successful prescribed HD with 2-needle cannulation of the AVF for three (3) continuous weeks.

Functional maturation will be identified if:

On the EndoAVF Dialysis page,

- Date of First 2-needle Cannulation of 3 Week Continuous Dialysis is not NULL and
- Date is before or on the cutoff date of the database lock.

Kaplan-Meier (KM) analysis will be used to estimate the time from HD AV access creation (the date of index procedure) to functional maturation. The following definition will be applied:

- If functional maturation occurs, the participant is considered as having the event, and date of first 2-needle cannulation of 3-week continuous dialysis will be used in the analysis.
- If the participant was transferred to PD, or had a kidney transplant, or had access discontinuation, or discontinued before a specific visit without attaining functional maturation, the participant is considered as censored the participant at the earliest date among these events (i.e. PD start date, kidney transplant date, date of access discontinuation, or last date of available study data including the unscheduled visit date).
- Otherwise, if the participant did not achieve functional maturation and has passed the specific visit window by the cutoff date of database lock, the participant will be censored at the end of the reporting time window (e.g., 180+30 = Day 210 for the 6-month reporting, 730+30 = 760 for the 24-month reporting) for this analysis. If the participant had access permanent abandonment prior to achieving functional maturation and has passed the specific visit window by the cutoff date of database lock, the participant will be censored at the date of permanent abandonment.

This endpoint will be evaluated on the AT population and on the AT population with endo AVF successfully used with 2 needles for hemodialysis (on the EndoAVF Dialysis page, Date endoAVF Successfully Used with 2 Needles for Hemodialysis is not NULL). The number of participants with events, number of participants censored, time to event (days), and proportion of participants with events along with the 95% CI will be presented at 6-weeks, 3-, 6-, 12-, 18-, and 24-months post creation using the KM method. For the 6-month reporting, the functional maturation rate up to 6-months (up to Day 210) will be presented. For the final reporting, the functional maturation rate up to 24-months (up to Day 760) will be presented.

Similar analysis will be done for successful prescribed HD with 2-needle cannulation of the AVF for two (2) continuous weeks.

### 5.3.5 Functional HD Usability

Functional HD usability is defined as dialyzed using successful 2-needle access of the AVF created as part of this clinical investigation for ≥75% of HD sessions over a continuous 28-day period.

Functional HD usability will be identified if:

On the EndoAVF Dialysis page,

- Percent of Sessions Using 2-Needle is ≥75 and
- Date of First 2-Needle Cannulation in 28 Day Period is not null and before the cutoff date of database lock.

Kaplan-Meier (KM) analysis will be used to estimate the time from HD AV access creation (the date of index procedure) to the first day of the 28-day period. The following definition will be applied:

- If functional HD usability occurs, the participant is considered as having the event, and date of first 2-needle cannulation in 28-day period will be used for the analysis.
- If the participant was transferred to PD, or had a kidney transplant, or had access discontinuation, or discontinued before the end of a specific visit window (e.g. Day 210 for 6 months post creation) without attaining functional HD usability, the participant is considered as censored at the earliest date among these events (i.e. PD start date, kidney transplant date, date of access discontinuation, last date of available study data including the unscheduled visit date).
- Otherwise, if the participant is still in the investigation without functional HD usability and have passed the specific visit window by the cutoff date of database lock, the participant will be censored at the end of the reporting time window (e.g., 180+30 = Day 210 for the 6-month reporting, 730+30 = 760 for the 24-month reporting) for this analysis. If the participant had access permanent abandonment prior to achieving functional HD usability and has passed the specific visit window by the cutoff date of database lock, the participant will be censored at the date of permanent abandonment.

This endpoint will be evaluated on the AT population and on the AT population with endo AVF successfully used with 2 needles for hemodialysis (on the EndoAVF Dialysis page, Date endoAVF Successfully Used with 2 Needles for Hemodialysis is not NULL). The number of participants with events, number of participants censored, time to event (days), and proportion of participants with events along with the 95% CI will be presented at 6-weeks, 3-, 6-, 12-, 18-, and 24-months post creation using the KM method. For the 6-month reporting, the functional HD usability rate up to 6-months (up to Day 210) will be presented.

